- Sign an IRB-approved informed consent document.
- Age ≥ 18 years.
- IPSS low- or intermediate-1–risk MDS, including CMML-1
- ECOG performance status of ≤ 3 at study entry.
- Organ function as defined below:
 - Serum creatinine ≤ 2 mg/dL
 - Total bilirubin $\leq 2 \times$ ULN
 - ALT (SGPT) $\leq 2 \times$ ULN
 - AST (SGOT) $\leq 2 \times$ ULN

- Women of childbearing potential must have a negative serum or urine pregnancy test within 7 days and will also need to use contraceptives. Men must agree not to father a child and agree to use a condom if his partner is of child bearing potential.

Exclusion Criteria:

- Breast feeding females
- Prior therapy with decitabine or azacitidine

V. Treatment plan

1. Study design

Transfusion-dependent subjects will be randomized to AZA 75 mg/m² IV/SC for 5 days, AZA 75 mg/m² IV/SC for 3 days, or DAC 20 mg/m² IV for 3 days on an even basis at the beginning, then, based on efficacy and following a Bayesian design, patients will be assigned to the superior arm.

Transfusion-independent subjects will be randomized to either BSC or one of the 3 arms mentioned above on an even basis at the beginning, then, based on efficacy and following a Bayesian design, patients will be assigned to the superior arm.

Transfusion-independent subjects assigned to BSC will be assigned to one of the 3 above arms once they start requiring blood transfusion. That would be considered an event.

Transfusion-dependent group will be defined as patients requiring blood transfusion for MDS or CMML-1 at any time.

2. Treatment plan

Patients will be randomized to receive:

Decitabine 20 mg/m² IV daily for 3 days (days 1-3) approximately every 28 days

or

Azacitidine 75 mg/m² SC or IV daily for 3 days (days 1-3) approximately every 28 days

or

Azacitidine 75 mg/m² SC or IV daily for 5 days (days 1-5) approximately every 28 days

or

BSC (for transfusion-independent subjects only)

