Patients may receive their second course of therapy without interruption, regardless of their degree of myelosuppression. After the first course of therapy, the interval between subsequent cycles of therapy could be shortened or prolonged at the discretion of the investigator. Subsequent cycles can be given prior to peripheral blood count recovery if considered to be in the best interest for the patient and after discussion with the principal investigator and the discussion documented in the patient's medical record. If study drug related prolonged myelosuppression (≥ 42 days of absolute neutrophil count [ANC] $< 1 \times 10^9/L$ and platelet count $< 30 \times 10^9/L$) is observed after cycle 2, subsequent cycles may be given at the next lower dose (DAC, 15 mg/m²/day, then 10 mg/m²/day, then 5 mg/m²/day; AZA, 56 mg/m²/day, then 37 mg/m²/day, then 18 mg/m²/day) after recovery (ANC $\geq 1 \times 10^9/L$ and platelet count $> 50 \times 10^9/L$) and subsequent cycles of

AZA. Granulocyte-colony stimulating factor for fever of unknown origin, infection, and/or ANC $<0.75 \times 10^9/L$ can be administered.

Dose reductions can also be made in other clinical situations where this step is considered to be in the best interest for the patient and after discussion with the principal investigator and the discussion documented in the patient's medical record. The following table is a suggestion for dose modifications in subsequent treatment courses:

Table 1: Dose levels adjustment

Dose level	AZA (mg/m ²)	DAC (mg/m ²)
-1	56	15
-2	37	10
-3	18	5

VI. BASELINE AND PER-TREATMENT EVALUATION

Baseline

1. A complete history and physical examination within 14 days prior to study entry.
2. CBC, differential platelet count.
3. Creatinine, bilirubin, ALT or AST,
4. Bone marrow aspirate and/or biopsy with cytogenetics (if bone marrow not done within 6 weeks and cytogenetics (if previously abnormal) within 3 months prior to study entry.

5. Serum or urine pregnancy test within 7 days of treatment start for women of childbearing potential
6. Documentation of frequency of transfusions (PRBC and Platelets) prior to start of each cycle
7. Documentation of any prior administration of growth factors and ESA

Prestudy laboratory tests must be obtained within 14 days of registration.

During therapy

1. CBC, differential, and platelet count once monthly prior to start of each cycle
(the differential may be omitted when the WBC is $< 0.5 \times 10^9/L$)

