Supportive measures such as prophylaxis for tumor lysis syndrome, analgesics, blood transfusions, antimicrobials and G-CSF for fever/infection are permitted as clinically indicated. Growth factor and ESA administration while on study will be documented.

VII. STUDY END POINTS

Primary:

1. Event-free survival rates of two different drugs DAC versus AZA on an abbreviated schedule and a standard arm of AZA given over 5 days in patients with low-risk MDS transfusion-dependent and to BSC in patients with low-risk MDS transfusion-independent. Events are defined as no response, loss of response, progression to higher risk category MDS, transformation to AML, discontinuation of therapy due to side effects, or death.

Secondary:

1. Overall improvement rate (OIR), defined as complete remission (CR), partial remission (PR), marrow CR (mCR), or hematologic improvement (HI), measured using each patient's best response with the 2 different agents. Response will be

assessed using the modified MDS International Working Group 2006 criteria. The best response within the first two cycles will be the OIR for each treatment arm that will be used in the adaptive randomization algorithm.

2. Transfusion independence (defined as being transfusion-free for ≥ 8 consecutive weeks between the first dose and study treatment discontinuation)
3. Cytogenetic response, if applicable
4. Clinical benefit
5. Duration of response
6. Time to transformation into AML
7. Overall survival
8. Safety profile

VII. CRITERIA FOR WITHDRAWAL

Reasons for withdrawal include:

- Withdrawal of consent or the subject refuses to continue treatment and/or procedures/observations.
- Relapse/progression unless the treating physician determines that the patient has achieved clinical benefit, at which time further therapy on protocol may be permitted with approval from the PI and the discussion documented in the patient's medical record.
- No response after at least 6 courses unless the treating physician determines that the patient has achieved clinical benefit, at which time further therapy on protocol may be permitted with approval from the PI and the discussion documented in the medical

record. A bone marrow biopsy and/or aspirate is required to confirm that the patient has not achieved a response.

- Intercurrent illness preventing further administration of protocol treatment,
- Unacceptable toxicity that in the opinion of the investigator makes continued therapy unsafe.

VIII. CRITERIA FOR RESPONSE

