The response criteria recommended by the MDS International Working Group 2006.

Responses must be verified, documented, and signed in the local medical record by the local PI. (Patients are considered non evaluable if they have received less than 2 courses of treatment, unless there is clear disease progression.)

Definitions:

Complete Response (CR):

Bone marrow: $\leq 5\%$ myeloblasts with normal maturation of all cell lines; persistent dysplasia will be noted

Peripheral blood:

Hgb ≥ 11 g/dL

Platelets $\geq 100 \times 10^9/L$

Neutrophils $\geq 1.0 \times 10^9/L$

Blasts 0%

Partial response (PR):

All CR criteria if abnormal before treatment except: bone marrow blasts decreased by $\geq 50\%$ over pretreatment but still $> 5\%$

Marrow CR:

Blasts \leq 5% and decrease by \geq 50% from baseline (baseline blasts should be above 5% to be eligible for marrow CR)

Hematologic Improvement (HI): (responses must last at least 8 weeks)

Erythroid response [HI-E; (if pretreatment Hgb $<$ 11 g/dL)]; Hgb increase by \geq 1.5 g/dL; Relevant reduction of units of RBC transfusions by an absolute number of at least 4 RBC transfusions/8 weeks compared with the pretreatment transfusion number in the previous 8 weeks. Only RBC transfusions given for a Hgb of \leq 9.0 g/dL pretreatment will count in the RBC transfusion response evaluation.

Platelet response [HI-P; ((if pretreatment Platelet count $<$ $100 \times 10^9 /L$)]: Absolute increase of $\geq 30 \times 10^9 /L$ for patients starting with $> 20 \times 10^9 /L$ platelets, or increase from $< 20 \times 10^9 /L$ to $> 20 \times 10^9 /L$ and by at least 100%.

Neutrophil response [HI-N; (pretreatment, ANC $< 1.0 \times 10^9 /L$)]: At least 100% increase and an absolute increase $> 0.5 \times 10^9 /L$

Progression/Relapse after hematological improvement: ≥ 1 of the following: $\geq 50\%$ decrement from maximum response levels in granulocytes or platelets; \downarrow in Hgb by ≥ 1.5 g/dL; transfusion dependence

Stable Disease: Not satisfying criteria for Complete Remission, Partial Response, Marrow CR, Hematologic Improvement or Progression/Relapse.

IX. REPORTING REQUIREMENTS

All adverse and serious adverse events will be recorded and reported according to the Leukemia-Specific Adverse Events (appendix A). The MD Anderson Leukemia

Department will report SAEs in accordance with MD Anderson IRB policies and procedures and Appendix A of the protocol.

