This is an adaptive randomized phase II trial for low-risk MDS patients. Regarding the patients transfusion status, patients can be categorized as transfusion dependent and transfusion independent patients. It is expected that there will be half of the transfusion-dependent patients and half of transfusion-independent patients. For transfusion dependent patients, the goal is to compare three treatment arms: 1) DAC, 2) AZA3 (treatment of 3 days), and 3) AZA5 (treatment of 5 days). For transfusion independent patients, the goal is to compare four treatment arms: 1) best supportive care (BSC) 2) DAC, 3) AZA3 (treatment of 3 days), and 4) AZA5 (treatment of 5 days). The primary outcome is event free survival (EFS) defined as the time from beginning of treatment till an event occurs or last follow-up. For transfusion independent patients, the events includes lack of response, requirement of blood transfusion, progression to advanced stages of disease, transformation into AML, discontinuation of therapy due to side effects, and death. The patients who change from transfusion independence to transfusion dependence under BSC will be enrolled in transfusion-dependent group and adaptively assign to the three treatment arms, that is, DAC, AZA3, or AZA5. For transfusion dependent patients, the events includes lack of response, progression to advanced stages of disease, transformation into AML, discontinuation of therapy due to side effects, and death.

Study design

The maximum number of patients accrued will be 240. There will be two parallel adaptive randomization trials for transfusion dependent (N=120) and transfusion independent (N=120) patients respectively. Since we are expecting patients under BSC

will eventually become the transfusion dependent, it is assumed that initially there will be 120 patients under transfusion-dependent group, and the total number increases to about 150 after enrolling the approximate 30 patients under BSC.

Part I Transfusion dependent patients (N=150)

Design

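### Part II has two different primary EFS event lists: start of transfusion counts in all four arms in Section XII, is absent from Section VII, and is stated only for BSC in Section V

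*Combined protocol and SAP*

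**What the plan says.** The combined protocol and SAP defines Part II event-free survival (EFS) in three places.

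- Section XII, General Description, under the primary outcome: "For transfusion independent patients, the events includes lack of response, requirement of blood transfusion, progression to advanced stages of disease". The same paragraph gives this group four arms: BSC, DAC, AZA3 and AZA5. Loss of response is not on the list.
- Section VII, Primary, one list for both groups: "Events are defined as no response, loss of response, progression to higher risk category MDS, transformation to AML", followed by stopping therapy for side effects and death. Transfusion is not on the list.
- Section V, Study design: BSC patients are assigned to a drug arm "once they start requiring blood transfusion. That would be considered an event". Nothing is said there about a transfusion on a drug arm.

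Transfusion reaches the Section VII list on drug by two indirect routes. A patient who never responds has an event as no response. A patient with hematologic improvement who later needs transfusion meets the relapse criterion in Section VIII, which includes "1.5 g/dL; transfusion dependence".

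Section V defines dependence broadly: "Transfusion-dependent group will be defined as patients requiring blood transfusion for MDS or CMML-1 at any time". Whether a platelet transfusion counts is not stated. The record scheduled in Section VI is "Documentation of frequency of transfusions (PRBC and Platelets) prior to start of each cycle". BSC has no cycles and no stated visit interval. Under Supportive care, "blood transfusions, antimicrobials and G-CSF for fever/infection are permitted as clinically indicated".

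**The concern.** The comparison with BSC is part of the primary objective, and becoming transfusion dependent is central to the BSC arm. Section XII expects about 30 BSC patients to move into Part I for this reason, and Table 6, scenario 1, averages 29 BSC patients.

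No text says which list governs. Staff who enter events on the trial website (Section X) could follow the formal end point section together with the BSC rule in Section V. A transfusion at month 2 would then end EFS on BSC but not, by itself, on drug. Those event records feed the allocation probabilities, the arm-dropping and selection rules, and the final logrank test. BSC would look worse with no true difference.

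**Working it through.** **1. The lists side by side**

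| Component | Section XII, Part II | Section VII | Section V |
|---|---|---|---|
| Start of transfusion | Yes, all four arms | Not named | Yes, stated for BSC only |
| Loss of response | Not named | Yes | Not addressed |
| No response, progression, AML, stopping for side effects, death | Yes | Yes | Not addressed |

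**2. One patient.** A drug-arm patient is transfused in cycle 2 during myelosuppression and later has a platelet response. Section XII scores an event at month 2. Section VII scores none, because the relapse criterion applies only after improvement. A BSC patient transfused at month 2 has an event under Sections V and XII. If the drug patient instead never responds, Section VII does record an event, but possibly months later: withdrawal for no response needs at least 6 courses, and 6 x 28 = 168 days is about 5.5 months.

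**3. The plan's own figures.** The Part II prior has mean 13.73/(2.14 - 1) = 12.04 months, against the stated 12. A simulation of Part II (3,000 runs, Section XII prior, square-root allocation with floor 0.1, 4 patients a month, 12 months' follow-up) selects AZA5 in 80.7% of runs at medians 12/12/12/24, against 79.7% in Table 6. With all medians 12 it selects BSC in 2.9% (Table 6: 3.7%) and places 29.8 patients on BSC (Table 6: 29).

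**4. Limiting case: transfusions on drug never counted.** Let every arm have median 12 months with transfusion counted, so the hazard is h = ln2/12 = 0.0578 per month. If a share f of it is never counted on drug, the drug median appears as 12/(1 - f): 13.3 months at f = 10% and 15.0 at f = 20%.

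**5. Delayed, not removed.** Let g be the transfusion share of the hazard and W = 5.5 months. Suppose a transfusion before W is scored as no response at W unless another event comes first, and a later one is scored when it happens as loss of response. The mean added time is

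D = [g/(1 - g)] x [(1 - e^(-hW))/h - e^(-(1-g)hW) x (1 - e^(-ghW))/(gh)]

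The exponential fit gives a median of 12 + ln2 x D when all events are observed.

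**6. Half delayed, half never counted.** The chance of a first event by transfusion before W is P = g x (1 - e^(-hW)) = 0.272g. If half of these patients respond later and the early transfusion is never scored, the fitted median is 12 + 0.5 x ln2 x D + 0.5 x P x 12/(1 - g).

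| g | D (months) | P | Median, step 5 | Median, step 6 |
|---|---|---|---|---|
| 20% | 0.145 | 0.054 | 12.1 | 12.5 |
| 40% | 0.296 | 0.109 | 12.2 | 13.2 |
| 50% | 0.373 | 0.136 | 12.3 | 13.8 |

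With the planned accrual (120/4 = 30 months) plus 12 months' follow-up as censoring, the fits are, to within 0.1 month, 12.1, 12.3 and 12.3 for step 5, and 12.6, 13.4 and 13.8 for step 6. The step 6 range corresponds to an effective f of 1 - 12/12.6 = 5% to 1 - 12/13.8 = 13%.

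**7. Effect on the adaptive design.** At f = 10%, inside that range, the same simulation places 26.9 patients on BSC instead of 29.8, and BSC ends closed in 0.26 of runs instead of 0.20 (Table 6: 0.235). This shows direction and rough size only. The simulation closes an arm to accrual when its probability of being best falls below 0.025, whereas Section XII ends the trial. Nor does it reproduce early selection (about 0.28 against 0.059 in Table 6, scenario 5), so the planning software evidently times its checks differently.

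**The case against.** The strongest reply is that Section XII already settles the matter. It is the specific Part II definition, it names no arm, and it sits in the section that governs allocation and analysis. Section V is consistent with it. Unequal counting arises only if staff combine Sections V and VII and set Section XII aside, which nothing directs. This stands as a limit on likelihood. It does not remove the conflict: Section VII is the formal end point section, and no order of precedence is given.

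It can also be said that most transfused drug patients fail under Section VII anyway. That largely stands and is why steps 5 and 6 give small shifts. Gaps remain, because the timing of no response is not fixed and transfusion dependence is a relapse criterion only after hematologic improvement. The loss-of-response mismatch acts mainly on drug-arm responders and in the opposite direction. The documents give nothing to size it.

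A reader might make three stronger inferences:

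- That drug medians could appear as 20 or 24 months, the AZA5 values in Table 6, scenarios 4 and 5. This needs 40% or 50% of the drug-arm hazard never to be counted, which nothing supports.
- That the event cannot be checked on BSC. A BSC transfusion surfaces through the switch to drug, and Section X asks for timely event recording. The case report form and the Data Quality Management Plan are not available here and may hold more.
- That discretion in ordering transfusions biases the result. This is possible, because no blinding is described and transfusion on BSC opens access to drug. The bias is not demonstrated, and its direction and size are unknown.

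**Conclusion.** The conflict is real and concerns the primary end point. Two components differ between Sections VII and XII, and Section V supports transfusion as an event only for BSC. Following Sections V and VII together would bias the comparison against BSC.

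The likely size is modest. Equal true medians of 12 months would appear on drug as about 12.1 to 12.3 months if uncounted transfusions are only delayed, and about 12.6 to 13.8 if half of the early-transfused patients later respond. These figures assume constant hazards, transfusion shares of 20% to 50%, no response scored at 5.5 months, and later transfusions counted as loss of response. The documents give none of the shares. The general expression 12/(1 - f) applies only to events that are never counted.

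On data capture, the supportable statement is that dating of the event is uneven across arms, not absent. The correction should be made because it is cheap and removes an ambiguity in the primary analysis, not because a large bias has been shown.

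**What to change.** 1. Use one identical Part II event list in Sections V, VII and XII, applied to all four arms. Add to Section VII the first transfusion given for MDS or CMML-1, naming the product (red cells only, or red cells and platelets). Add loss of response to Section XII, or remove it from Section VII so that neither list has it. The Part I list in Section XII also omits loss of response, so the same edit can cover it.
2. Record the date and product of every transfusion in every arm, with a monthly check on BSC.
3. Prespecify one sensitivity analysis of EFS without the transfusion component. State as a limitation that censoring BSC patients at crossover is informative.

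A hemoglobin threshold is optional and for the sponsor to decide. The existing rule, "9.0 g/dL pretreatment will count in the RBC transfusion response evaluation", concerns pretreatment transfusions in the erythroid response and need not become the event definition.

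The cost is one shared definition, two fields in the transfusion record, a monthly contact for BSC patients and one extra analysis. Table 6 needs no change if it already assumes one definition in all arms; the sponsor should confirm that the 12-month historical median refers to the list chosen. Discretion in ordering transfusions stays in the primary analysis.

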Patients will be randomized using a Bayesian adaptive algorithm. Patients will be randomized fairly among the three arms at the start of the trial (for the first 30 patients), that is, 10 patients per arm. Thereafter, as the trial progresses and data accrue, the randomization will become unbalanced in favor of the treatment that, on average, has better results in terms of event free survival. Therefore, each successive patient is more likely to receive the treatment with better results, on average. A minimum of 30 and a maximum of 150 patients will be accrued. There will be 12 months follow up after the last patient is accrued with an anticipated accrual rate of 5 patients per month.

Denote the event free survival for the patients in the three arms (DAC; AZA3; AZA5) as T_i for $i=1,2,3$. Assume the T_i is independent exponential with median μ_i . And each μ_i independently follows an inverse gamma distribution with parameter $\alpha=2.05$, $\beta=7.34$. The parameters were chosen to set the mean of the prior equal to 7 (the historical median EFS in months) and a variance of 1000. For each patient, the randomization probability for treatment arm i will be based on the posterior probability that it has the largest median EFS. For example, for arm 1, the posterior probability is $\pi_1=\Pr(\mu_1 > \mu_i)$ for $i=2,3$. In order to avoid aggressively favoring one arm too early in a large trial, instead of

assigning patients with posterior probability, we use its square root transformation as in the following formula to assign patients:

$$Aa = \frac{\sqrt{\pi_1}}{\sqrt{\pi_1} + \sqrt{\pi_2} + \sqrt{\pi_3}}, \text{ where } Aa \text{ is the probability of assigning patients to arm 1, } \pi_1 \text{ is}$$

the posterior probability that arm 1 is superior, etc.

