If at any point during the trial $Pr(\mu_i > \max\{u_j, \text{ for all } j \neq i\} | \text{data}) > 0.975$, the trial will be terminated and treatment i will be selected as superior. If at any point during the trial $Pr(\mu_i > \max\{u_j, \text{ for all } j \neq i\} | \text{data}) < 0.025$, then accrual to the arm i will be suspended, and will be reopen if in the future, the changes in other arms make this probability $Pr(\mu_i > \max\{u_j, \text{ for all } j \neq i\} | \text{data}) \geq 0.025$. If the maximum accrual is reached and $Pr(\mu_i > \max\{u_j, \text{ for all } j \neq i\} | \text{data}) > 0.8 (< 0.2)$, treatment i will be selected as superior (inferior). A treatment arm will be dropped at any point during the trial if $Pr(\mu_i > 7 | \text{data}) < 0.1$, for $i=1,2,3$. Table 3 given below summarizes operating characteristics of the design. The historical median EFS is assumed to be 7 months with the accrual rate of 5 patients per month. The trial will be stopped early and a treatment selected as being “better” if the probability that one treatment’s median EFS is larger than the other’s EFS exceeds 0.975. If the trial does not stop early and the maximum 150 patients are accrued, a treatment is selected as being “better” if the probability that one treatment’s median EFS is larger than the other’s EFS exceeds 0.8. A treatment arm will be dropped at any point during the trial if the probability that the treatment’s median EFS is larger than 7 months is less than 0.1. The “# of patients treated” row is

the average number of patients treated on a given arm under the given scenario.

When the medians all equal to 7 months (scenario 1), the probability of selecting one of the three arms (i.e., a false positive result) is at most 9.8%. The probability of selecting the best treatment (i.e., a true positive result) for scenario 2, when the medians EFS are 7, 7, and 12 months for the arms, respectively, are 0.7%, 0.7%, and 88%.

Table 3: simulation results (simulation=5000) for transfusion dependent patients with the minimum randomization probability set as 0.1 and tuning parameter as 0.5

		treatment		
		DAC	AZA3	AZA5
1	True Median EFS	7	7	7
	# of patients treated	40.1	40.6	40.5
	Pr(selected)	0.086	0.095	0.098
	Pr(selected early)	0.003	0.006	0.005
	Pr (stopped early)	0.321	0.317	0.316
2	True Median EFS	7	7	12
	# of patients treated	28.5	28.6	54.2
	Pr(selected)	0.007	0.007	0.88
	Pr(selected early)	0.0002	0.001	0.188

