Table 5: Operating characteristics of safety monitoring

True Toxicity Rate	Prob (stop the trial early)
0.15	0.04
0.2	0.25
0.25	0.68
0.3	0.94

Part II: Transfusion independent patients (N=120)

Design

Patients will be randomized using a Bayesian adaptive algorithm. Patients will be randomized fairly among the four arms at the start of the trial (for the first 40 patients), that is, 10 patients per arm. Thereafter, as the trial progresses and data accrue, the randomization will become unbalanced in favor of the treatment that, on average, has better results in terms of event free survival. Therefore, each successive patient is more likely to receive the treatment with better results, on average. A minimum of 40 and a maximum of 120 patients will be accrued. There will be 12 months follow up after the last patient is accrued with an anticipated accrual rate of 4 patients per month.

Denote the event free survival for the patients in the four arms (BSC; DAC; AZA3; AZA5) as T_i for $i=1,2,3,4$. Assume the T_i is independent exponential with median μ_i . And each μ_i independently follows an inverse gamma distribution with parameter $\alpha=2.14$, $\beta=13.73$. The parameters were chosen to set the mean of the prior equal to 12 (the historical median EFS in months) and a variance of 1000. For each patient, the randomization probability for treatment arm i will be based on the posterior probability that it has the largest median EFS. For example, for arm 1, the posterior probability is $\pi_1=\Pr(\mu_1 > \mu_i)$ for $i=2,3,4$. In order to avoid favoring one arm earlier in a large trial, instead of assigning patients with posterior probability, we use the following formula to assign patients:

$Aa = \frac{\sqrt{\pi_1}}{\sqrt{\pi_1} + \sqrt{\pi_2} + \sqrt{\pi_3} + \sqrt{\pi_4}}$, where Aa is the probability of assigning patients to arm 1, π_1 is the posterior probability that arm 1 is superior, etc.

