If at any point during the trial $\Pr(\mu_i > \max(u_j \text{ for all } j \neq i) | \text{data}) > 0.975$ (< 0.025), the trial will be terminated and treatment i will be selected as superior (inferior). If the maximum accrual is reached and $\Pr(\mu_i > \max\{u_j \text{ for all } j \neq i\} | \text{data}) > 0.8$ (< 0.2), treatment i will be selected as superior (inferior). A treatment arm will be dropped at any point during the trial if $\Pr(\mu_i > 12 | \text{data}) < 0.1$, for $i=1,2,3,4$. Table 6 given below summarizes operating characteristics of the design. The historical median EFS is 12 months. The tables below assume an accrual rate of 4 patients per month. The trial will be stopped early and a treatment selected as being “better” if the probability that one treatment’s median EFS is larger than the other’s EFS exceeds 0.975. If the trial does not stop early and the maximum 120 patients are accrued, a treatment is selected as being “better” if the probability that one treatment’s median EFS is larger than the other’s EFS exceeds 0.8. A treatment arm will be dropped at any point during the trial if the probability that the treatment’s median EFS is larger than 12 months is less than 0.1. The “# of patients treated” row is the average number of patients treated on a given arm under the given scenario. When the medians all equal to 12 months (scenario 1), the probability of selecting one of the three arms (i.e., a false positive result) is at most 3.7 %. The probability of selecting the best treatment (i.e., a true positive result) for scenario 5, when the medians TTP are 12, 12, and 24 months for the arms, respectively, are 0.1%, 0.04%, 0.2%, and 79.7%.

Table 6: simulation results (simulation=5000) for transfusion dependent patients with the minimum randomization probability set as 0.1 and tuning parameter as 0.5

			treatment		
		BSC	DAC	AZA3	AZA5
1	True Median EFS	12	12	12	12
	# of patients treated	29	28.9	28.8	28.6

	Pr(selected)	0.037	0.036	0.034	0.029
	Pr(selected early)	0.001	0.001	0.001	0.0004
	Pr (stopped early)	0.235	0.233	0.253	0.244
2	True Median EFS	7	7	7	7
	# of patients treated	14.2	14.3	14.3	14.4
	Pr(selected)	0.029	0.024	0.027	0.027
	Pr(selected early)	0.0002	0	0.0002	0.0002
	Pr (stopped early)	0.764	0.774	0.773	0.755
3	True Median EFS	7	12	15	20
	# of patients treated	13.2	24.2	32.3	42
	Pr(selected)	0	0.003	0.035	0.496
	Pr(selected early)	0	0.0004	0.003	0.036
	Pr (stopped early)	0.971	0.58	0.296	0.032
4	True Median EFS	12	12	12	20

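### The final rule labels an arm inferior when its probability of being best is below 0.2, which is weak evidence with three or four arms, and the plan reports no error rate for that label

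*Combined protocol and SAP*

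**What the plan says.** Section XII, Part I, Design (three arms) states the final rule for trials that reach maximum accrual: if the posterior probability that arm i has the longest median EFS is above 0.8 (below 0.2), "treatment i will be selected as superior (inferior"). Part II, Design (four arms) repeats the sentence with the same two cut-offs.

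The early rules are separate:
- In Part I, if that probability is below 0.025, "then accrual to the arm i will be suspended". The arm may reopen, and it is not called inferior.
- In Part II, the early rule reads "< 0.025), the trial will be terminated and treatment i will be selected as superior (inferior").
- In both parts, an arm is dropped if the probability that its median exceeds the historical value (7 or 12 months) is below 0.1.

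Tables 3 and 6 report the number treated, Pr(selected), Pr(selected early) and Pr(stopped early). The false-positive figures in the text, at most 9.8% and 3.7%, are the largest Pr(selected) values in scenario 1. No figure is given for the inferior label. The restatement of the final rule later in the same paragraph mentions only the choice of a better arm.

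**The concern.** With two arms, a probability of being best below 0.2 means the other arm's is above 0.8, so the two labels carry the same evidence. With more arms they do not. An arm can fall below 0.2 because the probability is shared among several similar arms, with nothing shown to beat it.

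Comparing EFS is the primary objective, so selection as inferior is a prespecified conclusion on the primary endpoint. It could be attached to a 3-day schedule, to 5-day azacitidine or to best supportive care on weak evidence. The plan gives no rate by which a reader could judge it.

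**Working it through.** **1. Arithmetic from the rule alone.** The probabilities of being best sum to 1 across arms.
- Average with equal arms: 1/3 = 0.333 in Part I and 1/4 = 0.25 in Part II.
- For no arm to be labelled inferior, every arm must be at 0.2 or above. The leader is then at most 1 − 2 × 0.2 = 0.6 in Part I and 1 − 3 × 0.2 = 0.4 in Part II. Only a near-tie avoids the label.
- If one arm exceeds 0.8, the others together have less than 0.2, so each is labelled inferior.

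**2. Simulation inputs (Section XII, Parts I and II, and the titles of Tables 3 and 6).**
- Part I: three arms, "Patients will be randomized fairly among the three arms at the start of the trial (for the first 30 patients"), maximum 150, 5 patients per month, reference median 7 months.
- Part II: four arms, "Patients will be randomized fairly among the four arms at the start of the trial (for the first 40 patients"), maximum 120, 4 patients per month, reference median 12 months.
- Both: 12 months' follow-up after the last patient, square-root adaptive randomization with a floor of 0.1, early cut-offs 0.975 and 0.025, futility drop at 0.1.
- Priors: inverse gamma (2.05, 7.34), mean 7.34/1.05 = 6.99; and inverse gamma (2.14, 13.73), mean 13.73/1.14 = 12.04.
- Model: exponential EFS. The posterior for each median is inverse gamma (α + events, β + ln 2 × follow-up time).

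**3. Reproducing the plan's own figures.**

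| Quantity | Plan | Simulation |
|---|---|---|
| Table 3, scenario 2, best arm selected | 0.88 | 0.87–0.89 |
| Table 6, scenario 5, best arm selected | 0.797 | 0.78 |
| Table 3, scenario 1, Pr(selected) per arm | 0.086–0.098 | 0.07–0.08 |
| Table 6, scenario 1, Pr(selected) per arm | 0.029–0.037 | 0.02–0.03 |
| Table 3, scenario 2, best arm selected early | 0.188 | 0.46–0.52 |
| Table 3, scenario 1, Pr(stopped early) | about 0.32 | 0.39–0.44 |

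Power is matched to within two points and null selection roughly. The early-stopping rows are not matched.

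**4. Inferior labels with all medians equal, among trials reaching maximum accrual.**

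| | Part I | Part II |
|---|---|---|
| At least one arm below 0.2 | about 85–92% | about 99% |
| Per arm | about 40% | about 52% |
| At least one arm, open arms only | about 36–50% | about 59–74% |
| Per open arm | about 22% | about 36% |
| An arm inferior and no arm superior | 69–74% | 90–92% |

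Open arms are those not already dropped for futility. The first, second and last rows count all arms. The expected number of labels per trial, all arms counted, is 3 × 0.40 = 1.2 in Part I and 4 × 0.52 = 2.1 in Part II.

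**5. Is this produced by the early rules?** With plain equal randomization and no early rules, the results are 39–40% per arm and 87% at least one in Part I, and 52–54% and 99% in Part II. The median probability of being best for an equal arm in Part II is then about 0.18, already under the cut-off. The cut-off itself produces the result.

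**6. All null trials.** If trials that stop before maximum accrual are included in the denominator, the final rule labels an arm in about 50–75% (Part I) and 62–96% (Part II), dropped arms counted. The ranges are wide because they depend on whether a trial continues with one arm left and, in Part II, on how the early termination below 0.025 is applied.

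**The case against.** **The rates are conditional.** A reader might infer that nearly every null trial wrongly labels an arm, or that each equal arm faces a coin flip. The first holds only for Part II trials reaching maximum accrual with dropped arms counted. For an arm already dropped for futility, the label adds little to a decision already taken. On the open-arm basis, half or more of null Part I trials at maximum accrual label nothing, and the per-arm rates are about 22% and 36%. This part of the objection stands.

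**The cut-off is not close to the null average in both parts.** It is 5 points below 0.25 but 13 points below 0.333. This also stands; Part I's rates are correspondingly lower.

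**Two equally good arms.** A reader might cite true medians of 7, 12 and 12 months, where one of the two best arms is called inferior in about 41% of simulated trials at maximum accrual. Nearly all of that occurs because the other arm is called superior; only about 4 points occur otherwise. Table 3, scenario 5, already shows this selection rate: 0.242 + 0.235 − (0.040 + 0.036) = 0.401 of all trials. It is a property of picking a winner and is no separate evidence against the 0.2 branch.

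**Consequence.** The label comes after accrual ends and has no action attached. The Analysis Plan also provides Kaplan–Meier estimates, a log-rank test and a Cox model. This lowers the severity. It does not remove the problem, because a prespecified conclusion would still be reported with an unstated error rate.

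**Simulator limits.** The early-stopping rows do not match the plan. That affects how many trials reach maximum accrual and which arms are still open. It barely moves the all-arm rate at maximum accrual, which also appears without any early rules.

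**Conclusion.** The point holds as a should-fix. Below 0.2 is weak evidence of inferiority with three or four arms. Even on the basis most favourable to the plan (open arms only), at least one equal arm is called inferior in over a third of null Part I trials and over half of null Part II trials that reach maximum accrual. With all arms counted, most null trials at maximum accrual name an inferior arm while naming no superior one. The quoted false-positive figures do not cover this.

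The figures assume exponential EFS, equal medians at the historical values, and the stated priors, accrual and follow-up. The open-arm and all-trial figures also depend on the handling of dropped arms, which the plan does not describe; hence the ranges.

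The documents do not support reading this as an error in superior selection, sample size or allocation. None of these uses the 0.2 branch.

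**What to change.** Delete the below-0.2 inferior branch from the final rule in Part I and Part II. The superior rule and every row of Tables 3 and 6 stay as they are. The cost is one clause per part, with no patients and no new simulation.

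If the sponsor wants an inferiority conclusion, it should name a reference arm for each part and define inferiority by the pairwise posterior probability that the arm's median is below the reference's. The cut-off should be calibrated by simulation, and the false-inferior rate under equal medians added to Tables 3 and 6, stating whether dropped arms are counted. The cost is one extra row per table. The choice of reference arm and of acceptable error rate belongs to the sponsor.
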